3 OBJECTIVES AND ENDPOINTS

OBJECTIVES	ENDPOINTS	JUSTIFICATION FOR ENDPOINTS
Primary		
To assess: a) safety and b) feasibility of using OrCam MyEye 2 by children with CLN3 or low vision.	
a) Adverse events b) Feasibility test, Feasibility questionnaire, and Device use diary (see Section 9.4.2)
 
The assessment periods will be 1 week at study site and 1 month at home.
	
a) Collection of adverse event data is a standard method for evaluating safety in clinical trials. b) No validated, standardized tool is available to evaluate the feasibility of augmentative communication devices such as the OrCam. We modified the feasibility questionnaire used in an adult study [26] to provide appropriate adaptation for the pediatric cohort.

Secondary		
To assess the efficacy of using the OrCam by	1) Function Test – Efficacy Scores (see Section 9.4.3)	No validated, standardized tool is available to evaluate the efficacy of augmentative communication

OBJECTIVES	ENDPOINTS	JUSTIFICATION FOR ENDPOINTS
children with CLN3 or low vision.	2) Ability questionnaire (see Section 9.4.3) The assessment periods will be 1 week at study site and 1 month at home.	devices such as the OrCam. We developed a Function Test based on the device's advertised functions, our observations of the pediatric cohort in the Natural History study, and the one used in an adult study [26], to provide age and ability appropriate assessments.
Exploratory		

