4.2 SCIENTIFIC RATIONALE FOR STUDY DESIGN

Currently, there is no device similar to the OrCam available or in accepted use for individuals with CLN3. In addition, there is also no data available on the use of this device in children with low vision. Thus, a combined cohort of pediatric participants with and without CLN3-related disorders will optimize recruitment potential, and provide preliminary information for evaluation of feasibility and efficacy in pediatrics, and specifically in individuals with CLN3-related conditions. To assess efficacy, we will use the study participants' baseline data as controls. This option encompasses the least number of confounding factors for a cohort of small size.

In the CLN3 natural history study (18-CH-0002), accrual rate averages at 8-10 per year. Not all of these individuals will meet the eligibility criteria for this proposed study. However, we anticipate, based on experience with interventional trials of other rare diseases, that families hesitant to participate in an observational study would be more open to participating in an interventional study. Given these considerations, we anticipate an accrual rate of 5 participants per year and a reasonable potential to enroll 20 CLN3 participants over 2-3 years. We have also discussed potential eligible participants with local Ophthalmology groups (Howard University, Johns Hopkins, NEI), and the anticipated number for pediatric individuals with low vision and not CLN3-related condition is estimated to be in the same range. We plan to screen up to 50 participants.

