9.4.3 Analysis of the Secondary Endpoint(s)

Function Test – Efficacy Scores

Data analysis. Participants' scores will be the sum of items 1 to 7 combining levels a & b and will range from 0 to 14, and the mean duration to complete each task. Analysis will consist of change in scores and mean duration to complete each task from baseline to 1 week and 1 month). No formal statistical tests will be conducted. Interpretation of results will be rule-based.

Rules for data interpretation. Device use is efficacious if at 1-week or 1-month compared to baseline:

- 25% or more of total number of participants increased score by at least 30%
- 25% or more of total number of participants decreased time by at least 30%

Below are some simulations of the power of a paired-sample test for change from baseline, using a sample size of 10 participants. This provides a sense of the possible characteristics of the data and for justifying the sample size.

Simulations for tasks-completed scores

Each simulation study used 1000 replications with $N = 10$. For each replication, baseline and post-baseline sets of scores were randomly generated. Means, standard deviations, and paired-samples t-tests of difference scores (Post-baseline – Baseline)

were computed. Power was computed by the percent of replications (out of 1000) with t-test p-values less than or equal to 0.05. Baselines were generated by randomly selecting, with replication, scores from 0 to 5 with equal probability, 1/6. The baseline range matched the baseline values reported in the adult study. Post-baseline scores included a specified number of baseline cases randomly selected without replacement to improve by 30% (Baseline \times 1.30). Cases with baseline values = 0 were excluded from random selection since percentage change from 0 is undefined.

Simulation 1. Based on the decision rule of 25% of total participants, 3 cases (rounded up since 25% of N= 10 is 2.5) were randomly selected to improve 30% from baseline and the other 7 cases did not improve. *Results: power = proportion of 1000 p-values <= 0.05 = 0.37.*

Simulation 2. 3 cases randomly selected to improve 30% and 7 cases improved by 1 point. *Results: power = proportion of 1000 p-values <= 0.05 = 1.0.*

Simulation 3. 4 cases randomly selected to improve 30% and 6 cases did not improve. *Results: power = proportion of 1000 p-values <= 0.05 = 0.95.*

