Simulation 4. 4 cases randomly selected to improve 30%, 6 cases improved by 1. *Results: power = proportion of 1000 p-values <= 0.05 = 1.0.*

Simulation 5. 2 cases randomly selected to improve 30% and 8 cases did not improve. *Results: power = proportion of 1000 p-values <= 0.05 = 0.00.*

Simulation 6. 2 cases randomly selected to improve 30%, 8 cases improved by 1. *Results: power = proportion of 1000 p-values <= 0.05 = 1.0.*

Simulations with baseline values 1 to 5, # cases improving 30%: 2 to 5; # cases improving by 1: 0 to 3; # cases no improvement: 4 to 8. (For any simulation run, # cases improving 30% + #cases improving by 1 + # cases not improving = 10).

Results: These simulations correct for the problem that percentage improvement is undefined when baseline = 0. When stipulating that percentage improvement is 30% for as few as 2 or 3 cases, power is greater than .99 when only 1 to 3 other randomly selected cases improve by 1 from baseline. Power will be higher if participants' scores improve more than 1 over baseline.

Based on these simulations, a test of efficacy using a paired-samples t-test with N = 10 would be adequately powered provided that post-baseline scores are likely to improve from baseline. Whether or not a sample of 10 is large enough to make conclusions about different characteristics of the sample group is not addressed.

Ability Questionnaire

Data analysis. Proportions of participants with scores 3 or greater in all items from 1-12. No formal statistical tests will be conducted. Interpretation of results will be rule-based.

Rules for data interpretation. Device use is efficacious if there is a 25% increase in the proportion of participants scoring 3 or greater in all items at 1-week or 1-month as compared to baseline.

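### The 9.4.3 powers rest on an adult-study baseline range not justified for the 0-14 Function Test and on an unstated one-sided test, and the above-.99 claim fails in one of its own cases

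*Combined protocol and SAP*

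**What the plan says.** On the score, 9.4.3 states: "Participants' scores will be the sum of items 1 to 7 combining levels a & b and will range from 0 to 14". The control is the child's own first assessment. Section 4.2: "To assess efficacy, we will use the study participants' baseline data as controls".

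On the simulated baseline, 9.4.3 states: "Baselines were generated by randomly selecting, with replication, scores from 0 to 5 with equal probability, 1/6". The justification follows: "The baseline range matched the baseline values reported in the adult study". A second set of runs uses 1 to 5. Selected cases have their baseline multiplied by 1.30, and the others gain 1 point or nothing. N is 10, and a replication counts as a success when the paired t-test p-value is at most 0.05. Whether the test is one- or two-sided is not said.

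The printed powers for Simulations 1 to 6 are 0.37, 1.0, 0.95, 1.0, 0.00 and 1.0. For the 1-to-5 runs the text says "When stipulating that percentage improvement is 30% for as few as 2 or 3 cases, power is greater than .99" when 1 to 3 further cases gain one point. It concludes that 10 participants give adequate power if scores are likely to improve.

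On the origin of the test, Section 3 says: "We developed a Function Test based on the device's advertised functions, our observations of the pediatric cohort in the Natural History study", with the adult study's test as a third source. Section 9.2 says no earlier data exist for these measures, yet reports the adults' 70% mean gain as a gain on the Function Test.

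**The concern.** The simulations are the only power figures in the plan, and 9.4.3 offers them partly to justify the sample size. Their baseline comes from neurologically intact adults, whereas the trial's test was adapted for children and has a 14-point scale. Nothing explains why these children should start between 0 and 5.

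This matters because the recipe mixes a proportional gain with a fixed one, so the t-statistic depends on where baselines lie and how they are spread. If the printed powers hold only under that baseline and an unstated one-sided test, a reader planning the later efficacy trial that 9.2 foresees could rely on figures that do not carry over.

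**Working it through.** **Inputs (all from 9.4.3).** N = 10; whole-number baselines with equal probability; k cases at +30%, p cases at +1, the rest unchanged; zero baselines not selectable for the +30% gain; threshold 0.05.

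**Formula.** Let S be the sum of the ten gains, Q the sum of their squares, and r = S²/Q. For N = 10, t = 3S/√(10Q − S²), so t² = 9r/(10 − r).
- One-sided 0.05, 9 df: critical t = 1.833, squared 3.360. Significance needs r ≥ 33.60/12.36 = 2.72.
- Two-sided 0.05: critical t = 2.262, squared 5.117. Significance needs r ≥ 51.17/14.12 = 3.62.
- r can never exceed the number of children with a non-zero gain.

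The number of possible baseline combinations is finite, so each power below is the exact share of equally likely combinations that meet the threshold. Simulations 2, 4 and 6 were simulated.

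**Reproducing the plan, baseline 0-5.**
- Simulation 5 (k = 2): r ≤ 2, so power is 0 either way. Printed 0.00.
- Simulation 1 (k = 3): r ≤ 3 < 3.62, so two-sided power is exactly 0. One-sided, 47 of 125 combinations pass: 0.376. Printed 0.37.
- Simulation 3 (k = 4): one-sided 605 of 625 = 0.968; two-sided 0.309. Printed 0.95.
- Simulations 2, 4 and 6: 1.00 either way.

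The printed set therefore fits a one-sided test only. The 0.95 is 0.018 below the exact value, about 3 Monte Carlo standard errors (√(0.968 × 0.032/1000) = 0.0056). Some detail of the code may not be recorded, but the two-sided 0.31 is far away.

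**The above-.99 statement on its own 1-5 baseline.** For k = 2, p = 1 the gains are 0.3a, 0.3b and 1, with a and b from 1 to 5. Baselines 1 and 3, for example, give S = 2.2, Q = 0.09 + 0.81 + 1 = 1.90 and r = 4.84/1.90 = 2.55, which fails. Every pair containing a baseline of 1 fails (9 of 25 ordered pairs), and so does 2 with 5 (2 of 25). Power is 14/25 = 0.56. The cells 2+2, 2+3, 3+1, 3+2 and 3+3 are 1.00 one-sided. Two-sided, 2+1 is 0, 2+2 is 0.64 and 3+1 is 0.42.

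**Same recipe, uniform baselines over the full scale (assumption), one-sided.**

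| Scenario | Plan states | 0-5 or 1-5 | Full scale, fractional, no cap | Fractional, cap 14 | Whole-number, cap 14 |
|---|---|---|---|---|---|
| Simulation 1 (3+0) | 0.37 | 0.376 | 0.333 | 0.293 | 0.359 |
| Simulation 3 (4+0) | 0.95 | 0.968 | 0.865 | 0.770 | 0.846 |
| 2+1 | above .99 | 0.560 | 0.122 | 0.208 | 0.152 |
| 2+2 | above .99 | 1.000 | 0.837 | 0.800 | 0.800 |
| 2+3 | above .99 | 1.000 | 0.990 | 0.969 | 0.970 |
| 3+1 | above .99 | 1.000 | 0.838 | 0.771 | 0.802 |
| 3+2 | above .99 | 1.000 | 0.988 | 0.958 | 0.966 |
| 3+3 | above .99 | 1.000 | 1.000 | 0.994 | 0.996 |

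Simulations 2, 4 and 6 stay at 1.00 and Simulation 5 at 0.00. Whole-number means a 30% gain rounded up to the next integer.

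**Why it moves.** In the pure +30% scenarios r is unchanged if all scores are rescaled, so only the spread relative to the mean counts. That ratio is 1.41/3 = 0.47 on 1-5, 4.03/7.5 = 0.54 on 1-14 and 1.71/7.5 = 0.23 on 5-10. On 5-10, Simulation 1 rises to 0.99 and Simulation 3 to 1.00. In the mixed cells the average +30% gain is 0.3 × 3 = 0.9 on 1-5, close to the fixed +1, but 0.3 × 7.5 = 2.25 on 1-14, so the gains become unequal and r falls.

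**The case against.** A baseline of 0 to 5 is possible on a 0-14 scale. With acuity worse than 20/200 required and intellectual disability common in CLN3, low starting scores are plausible, and uniform 0-14 is no better grounded. This stands: the documents show neither range to be right. It leaves the printed powers conditional, not refuted.

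The practical weight is also small. The Function Test is secondary and judged by a 25%/30% rule without a formal test, and 9.2 says power cannot be determined. Section 9.4.3 presents the runs partly to give a feel for the data and makes its conclusion conditional on improvement. Section 4.1 analyses all 30 participants together. With 8 of 30 at +30% (25% of 30 is 7.5, rounded up), simulated power is at least 0.99 on both the 0-5 and 0-14 ranges. All of this stands and sets the severity. It does not answer the unstated sidedness or the failing 2+1 case, which are faults on the plan's own terms.

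A reader might infer that a wider scale necessarily lowers power. The 5-10 result shows otherwise. A reader might also infer that fractional scores such as 1.3 are impossible. The 0-14 sum suggests whole item-levels, but the content of Appendix C is not available to confirm it.

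**Conclusion.** The point holds as a minor correction of stated figures. Two parts need no assumption about the children: the printed powers fit only a one-sided test that is not declared, and the above-.99 claim is false for 2+1 on the plan's own 1-5 baseline (0.56). The third part is conditional. With uniform full-scale baselines, Simulation 3 is about 0.77 to 0.87, Simulation 1 about 0.29 to 0.36, 2+2 about 0.80 to 0.84, 3+1 about 0.77 to 0.84, 2+1 about 0.12 to 0.21, and 2+3 and 3+2 about 0.96 to 0.99. A middle range of 1-10 gives 0.94 to 1.00 for 2+2 and 3+1, and a tight mid-range baseline raises power.

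The documents do not support reading this as showing that the trial is underpowered: the children's baseline distribution is unknown, no formal test is planned for this endpoint, and planned enrolment is three times the simulated N.

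**What to change.** In 9.4.3:
- State whether the test is one- or two-sided.
- Rerun on attainable scores within 0-14, capped at 14, for low (0-5), middle (0-10) and full (0-14) baselines, and include the 2+1 cell.
- Replace the printed powers, the above-.99 statement and the adequate-power conclusion with the resulting range, labelled as conditional on the assumed baseline.

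In 9.2, attribute the 70% adult gain to the adult study's own test.

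The cost is a short rerun and some rewording. Some stated powers will look less favourable. Enrolment, conduct and the rule-based analysis do not change.

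### Section 9.4.3 claims power above .99 for a simulated case where it is about 0.56 (one-sided) or 0 (two-sided), and never says which test was run

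*Combined protocol and SAP*

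**What the plan says.** Section 9.4.3 interprets the Function Test by rule: "No formal statistical tests will be conducted". It then reports simulations of a paired t-test on change from baseline with 10 participants and gives their purpose: "This provides a sense of the possible characteristics of the data and for justifying the sample size". Power is the share of 1000 replications "with t-test p-values less than or equal to 0.05". For Simulations 1 to 6, "Baselines were generated by randomly selecting, with replication, scores from 0 to 5 with equal probability, 1/6". A child who improves 30% has a difference of 0.3 times baseline.

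Simulation 1 (3 children at +30%, 7 unchanged) reports "power = proportion of 1000 p-values <= 0.05 = 0.37". Simulation 3 (4 at +30%, 6 unchanged) reports "power = proportion of 1000 p-values <= 0.05 = 0.95". Simulation 5 (2 at +30%, 8 unchanged) reports 0.00.

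A second set of runs uses baselines 1 to 5 and the grid "cases improving 30%: 2 to 5; # cases improving by 1: 0 to 3; # cases no improvement: 4 to 8", with the three counts adding to 10. Its summary is that, with 30% improvement in as few as 2 or 3 children, "power is greater than .99 when only 1 to 3 other randomly selected cases improve by 1 from baseline". The section then concludes that a paired t-test with N = 10 has adequate power, provided scores are likely to improve.

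**The concern.** The summary sentence makes no exception, yet its lowest combination is 2 children at +30%, 1 at +1 and 7 unchanged (written 2+1 below). Three small positive differences among ten give a paired t-test little to work with. Simulation 1 also has three improvers, and its printed power is only 0.37, so a jump to above .99 needs checking.

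Neither 9.4.1 nor 9.4.3 says whether the test is one-sided or two-sided, and the answer turns on this. Section 9.4.1 also treats p between 0.05 and 0.10 as a trend. If that p is two-sided, every success counted in Simulation 1's 0.37 would be only a trend.

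What is at stake is the sample-size justification. Section 9.2 gives no power figure, so these runs are the only numerical support.

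**Working it through.** **Inputs (9.4.3).** N = 10, paired t-test with 9 df, rejection at p ≤ 0.05. Differences are 0.3 × baseline for the 30% improvers, 1 for the one-point improvers and 0 for the rest. Critical t is 1.833 one-sided and 2.262 two-sided. Baselines 1 to 5 are taken as equally likely; the plan states equal probability only for the 0-to-5 runs.

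**Formula.** t = mean(d) / (s_d / √10). Once the number of one-point improvers is fixed, t depends only on the baselines of the k children improving 30%, so all 5^k combinations can be listed and power is exact.

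**Step 1: reproduce the printed figures.** Children with baseline 0 are not selected for 30% improvement, so the same enumeration serves Simulations 1 to 6. The chance of fewer than 4 non-zero baselines among 10 is 0.0003 and is ignored.

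| Run | Printed | Exact one-sided | Exact two-sided |
|---|---|---|---|
| Simulation 1 (3+0) | 0.37 | 47/125 = 0.376 | 0 |
| Simulation 3 (4+0) | 0.95 | 605/625 = 0.968 | 193/625 = 0.309 |
| Simulation 5 (2+0) | 0.00 | 0 | 0 |
| Simulations 2, 4, 6 | 1.0 | 1.00 | 1.00 |

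In Simulation 1 the largest possible t is 1.964 (two-sided p 0.081), so a two-sided 0.05 test would never reject. The printed 0.37 therefore implies a one-sided 0.05 test, or equivalently a two-sided 0.10 test. The match for Simulation 3 is looser: if true power is 0.968, the chance of 954 or fewer rejections in 1000 is 0.010.

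**Step 2: upper bound for 2+1.** With m equal non-zero differences among N, t = √[m(N − 1)/(N − m)]. Unequal differences give less. For m = 3 and N = 10, t = √(3 × 9/7) = √(27/7) = 1.964. With the possible scores the maximum comes from baselines 3 and 3:

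- Differences 0.9, 0.9, 1 and seven zeros; mean 0.28; sum of squares 2.62.
- s² = (2.62 − 2.8²/10)/9 = 1.836/9 = 0.204.
- t = 0.28/√(0.204/10) = 1.960, two-sided p = 0.0816.

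This is below 2.262, so two-sided power is exactly 0 whatever the baselines.

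**Step 3: one-sided power for 2+1.** Of the 25 ordered baseline pairs, 11 fall below 1.833: the 9 that contain a 1 (largest t 1.754, for 1 and 3), plus (2,5) and (5,2) with t = 1.807. Power = 14/25 = 0.56.

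**Step 4: dependence on the baseline assumption.** Weights 5:4:3:2:1 on baselines 1 to 5 give 0.41; weights 1:2:3:4:5 give 0.78. Every pair containing a 1 fails. With p₁ the probability of a baseline of 1, power above .99 therefore needs 1 − (1 − p₁)² < 0.01, so p₁ < 0.005.

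**Step 5: all cells covered by the .99 sentence.**

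| Cases at +30% and at +1 | One-sided | Two-sided |
|---|---|---|
| 2+1 | 0.56 | 0 |
| 2+2 | 1.00 | 16/25 = 0.64 |
| 2+3 | 1.00 | 1.00 |
| 3+1 | 1.00 | 52/125 = 0.416 |
| 3+2 | 1.00 | 1.00 |
| 3+3 | 1.00 | 1.00 |

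In the rest of the grid, 2+0 and 3+0 are as in Simulations 5 and 1, and 4+0 is as in Simulation 3. The cells 4+1, 4+2, 5+0 and 5+1 are 1.00 one-sided, and 0.966, 1.00, 0.901 and 1.00 two-sided.

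**The case against.** The strongest reply is that nothing in the trial turns on this number. The Function Test has no planned p-value, 9.2 says power cannot be calculated, and 4.1 assesses the primary and secondary objectives on all 30 participants. At that size the problem disappears: the same proportions as 2+1 (6 at +30%, 3 at +1, 21 unchanged) give power 1.00 one-sided and two-sided. So does 4+2+14 at N = 20, the size of the CLN3 cohort. This stands and sets the severity. The error bears on the N = 10 argument and does not show that 30 participants are too few. It also makes the trend-band point hypothetical for this endpoint.

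A second reply is that the adequacy sentence carries a proviso, and that scores are hardly likely to improve when 7 or 8 of 10 children do not. That is a possible reading. But the proviso does not say how many children must improve, and Simulation 1 is the plan's own illustration of its 25% rule. Naming the exceptions removes the doubt.

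Third, the one-sided reading is an inference that rests mainly on Simulation 1, since Simulation 3 fits less closely, and 0.56 assumes equally likely baselines. Both points are fair. Neither rescues the sentence: 2+1 fails on either sidedness, and under any baseline distribution that gives a score of 1 more than a negligible probability.

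**Conclusion.** The concern holds, at minor severity. The claim of power above .99 is wrong for 2+1, where exact power is 0.56 one-sided (0.41 to 0.78 under the two other weightings tried) and 0 two-sided. The two-sided zero needs no assumption about baselines; the 0.56 assumes that scores 1 to 5 are equally likely. A gap of this size cannot be simulation noise with 1000 replications.

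The sidedness is undeclared and decides how far the error reaches: one of the six cells in the sentence if one-sided, three if two-sided. The printed 0.37 points to a one-sided test. The low results of Simulations 1 and 5 are already printed in the plan, so what misleads is the summary sentence and the general conclusion drawn from it.

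**What to change.** In 9.4.3:

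1. State whether the simulated t-test is one-sided at 0.05, as the printed 0.37 implies, or rerun it two-sided. State the baseline distribution used for the 1-to-5 runs.
2. If one-sided, except 2+1 from the .99 sentence, report it as about 0.56, and recheck the 0.95 for Simulation 3 (exact 0.968). If two-sided, report Simulation 1 as 0.00, Simulation 3 as 0.31, 2+1 as 0.00, 3+1 as 0.42 and 2+2 as 0.64, and limit the .99 claim to 2+3, 3+2 and 3+3.
3. Qualify the N = 10 conclusion: it does not hold for Simulation 1, Simulation 5 or 2+1. If two-sided, add Simulation 3, 3+1 and 2+2 to the exceptions.

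The cost is two added phrases and two reworded sentences. A rerun is needed only if the two-sided test is chosen, or to recheck Simulation 3. Enrolment, endpoints and decision rules stay as they are.

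### Section 9.4.3 says power rises when scores improve by more than 1 point, but in the plan's own simulation model it falls or stays at 1.00; the adjacent claim of power above .99 also fails for one scenario it covers (0.56)

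*Combined protocol and SAP*

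**What the plan says.** Section 9.4.3 of the combined protocol and SAP offers simulations of a paired-sample test with 10 participants, partly to justify the sample size. The test is described as "Means, standard deviations, and paired-samples t-tests of difference scores", and the success criterion is given as "Power was computed by the percent of replications (out of 1000) with t-test p-values less than or equal to 0.05". Whether the p-values are one-sided or two-sided is not stated.

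Simulations 1 to 6 draw baseline "scores from 0 to 5 with equal probability, 1/6". Their printed powers are 0.37, 1.0, 0.95, 1.0, 0.00 and 1.0. A second set uses baselines 1 to 5, with 2 to 5 cases gaining 30%, 0 to 3 cases gaining 1 point, and 4 to 8 cases unchanged. For 2 or 3 cases at 30%, the plan reports that "power is greater than .99 when only 1 to 3 other randomly selected cases improve by 1 from baseline". It then adds "Power will be higher if participants' scores improve more than 1 over baseline" and concludes that a sample of 10 is adequately powered provided scores are likely to improve.

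No run with a fixed gain above 1 point is described. The same section says that the Function Test will be judged by rules, without formal tests.

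**The concern.** A reported power above .99 has almost no room to rise, so the sentence serves as reassurance that the printed figures are conservative. The paired t statistic divides the mean change by its standard error. When most cases do not change at all, enlarging the gain of one or two cases can increase the standard deviation of the differences faster than the mean, and t then falls. If so, the plan misstates how its own test behaves, and the printed powers sit near the best case instead of at a floor. At stake is whether the simulations support the sample size in the way the text says. The Function Test score runs from 0 to 14, so gains above 1 point are possible.

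**Working it through.** **Inputs, all from Section 9.4.3.** N = 10. A 30% improver changes by 0.3 × baseline, which is 0.3 to 1.5 points for baselines 1 to 5. Other improvers change by a fixed g (the plan uses g = 1). The remaining cases change by 0. Below, 3+1 means three cases at 30% and one other at g.

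**Formula.** t = mean / (SD/√10) on 9 degrees of freedom. Critical values at 5% are 1.833 (one-sided) and 2.262 (two-sided). A zero baseline cannot be selected for a 30% gain, so the selected baselines are uniform on 1 to 5. Power for k such cases is then the share of the 5^k equally likely combinations that exceed the critical value.

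**Step 1: reproduce the printed powers.**

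| Simulation | Printed | One-sided | Two-sided |
|---|---|---|---|
| 1 (3 at 30%, 7 unchanged) | 0.37 | 0.376 | 0.00 |
| 2 (3 at 30%, 7 at +1) | 1.0 | 1.00 | 1.00 |
| 3 (4 at 30%, 6 unchanged) | 0.95 | 0.968 | 0.309 |
| 4 (4 at 30%, 6 at +1) | 1.0 | 1.00 | 1.00 |
| 5 (2 at 30%, 8 unchanged) | 0.00 | 0.00 | 0.00 |
| 6 (2 at 30%, 8 at +1) | 1.0 | 1.00 | 1.00 |

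Only the one-sided column matches, to within 2 percentage points. There is also a direct argument. With three improvers and seven zeros, t is largest when the three gains are equal, and it is then √(3 × 9 / 7) = 1.96. That is below 2.262, so Simulation 1 could never reach two-sided significance, yet 0.37 is printed.

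**Step 2: the claim of power above .99 at g = 1.** One-sided power is 1.00 for 2+2, 2+3, 3+1, 3+2 and 3+3. For 2+1, 14 of the 25 baseline combinations exceed 1.833, so power is 14/25 = 0.56. The 2+1 case also has three improvers and seven zeros, so the ceiling of 1.96 applies and two-sided power is 0.00. With seven unchanged cases, 2+1 lies inside the plan's stated ranges.

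**Step 3: raise the other cases' gain above 1 (one-sided 5%).**

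| Scenario | +1 | +2 | +3 | +4 | +5 |
|---|---|---|---|---|---|
| 2+1 | 0.56 | 0.24 | 0.00 | 0.00 | 0.00 |
| 2+2 | 1.00 | 0.96 | 0.88 | 0.68 | 0.40 |
| 2+3 | 1.00 | 1.00 | 1.00 | 1.00 | 1.00 |
| 3+1 | 1.00 | 0.87 | 0.48 | 0.16 | 0.03 |
| 3+2 | 1.00 | 1.00 | 0.99 | 0.97 | 0.85 |
| 3+3 | 1.00 | 1.00 | 1.00 | 1.00 | 1.00 |
| 4+1 | 1.00 | 0.99 | 0.91 | 0.68 | 0.33 |
| 5+1 | 1.00 | 1.00 | 0.99 | 0.93 | 0.76 |

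The 4+2 scenario stays at 0.99 or above. Power never exceeds its +1 value in any scenario with 2 to 5 cases at 30% and 1 to 3 others.

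**Step 4: why.** Take three gains of 0.9 and one of g. The mean is (2.7 + g)/10.

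| g | Mean | SD | t |
|---|---|---|---|
| 1 | 0.37 | 0.479 | 2.45 |
| 2 | 0.47 | 0.685 | 2.17 |
| 3 | 0.57 | 0.953 | 1.89 |
| 4 | 0.67 | 1.245 | 1.70 |
| 5 | 0.77 | 1.546 | 1.58 |

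The mean roughly doubles while the SD more than triples. If all gains are multiplied by the same factor, mean and SD scale together and t does not change.

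**The case against.** The strongest reply is that the result belongs to a model without noise. In the plan's simulations every non-improver changes by exactly 0, which real scores will not do. If random change is added to all ten cases, the plan's sentence often has the right direction. The documents give no SD for such change, so these values are assumptions:

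- SD 1: one-sided power for 3+3 rises from about 0.42 at +1 to about 0.78 at +4.
- SD 2: even 3+1 rises, from about 0.13 to about 0.17.
- SD 0.5: the pattern is mixed. For +1 to +4, 3+1 goes 0.41, 0.44, 0.38, 0.28, while 3+3 rises from 0.79 to 0.97.

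This stands, and it limits the point. A reader might infer that larger gains in a few participants reduce the power of a paired t-test in general; that does not follow. What can be said is that the sentence is presented as a consequence of these simulations, and under their model it is wrong.

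Sidedness matters too. Two-sided, 3+1 starts at 0.42, rises briefly to 0.49 at +1.1, and falls to 0.16 at +2. So the statement that power never rises is a one-sided result.

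Finally, the practical weight is small. Section 9.4.3 rules out formal tests for this endpoint, Section 9.2 says power could not be determined, and the study plans to enrol 30 participants, not 10. No decision rule depends on the sentence.

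**Conclusion.** The point holds in a limited form. Under the plan's own model and the one-sided test that its figures imply, power falls or stays at 1.00 as the other cases' gain exceeds 1 point. The steepest fall from 1.00 is in 3+1, down to 0.03 at +5. Separately, the claim of power above .99 is wrong for 2+1, where power is 0.56.

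Two stronger readings are not supported. First, a reader might infer that any gain above 1 point cuts power to about a half or less. In 3+1 that takes a one-sided test and a gain of about 3 points; power is still 0.87 at +2, and 2+3 and 3+3 do not fall at all. Second, a reader might infer that the error will pass into the design of the later trial. Section 9.2 says that the pilot data will inform that power calculation; it does not say that this sentence will.

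The conclusion assumes the described model without rounding of the 30% gains and with no change in non-improvers. The consequence is confined to the sample-size justification, so the priority is low.

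**What to change.** In Section 9.4.3:

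1. Delete the sentence saying that power increases with gains above 1 point. Do not replace it with a general statement about the paired t-test, because the direction depends on how much random change is present.
2. State that the printed powers are one-sided at 5%.
3. Restate the claim of power above .99 so that it excludes 2+1, and report 0.56 for that scenario.
4. Add rows for gains of 2 to 5 points, give the lowest power found, and label them as specific to a model in which non-improvers do not change.

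The cost is a few sentences and a rerun of the existing simulation code, with no new data or participants. The downside is that the stated power becomes less favourable.
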